While RA is recommended for all women no later than age 30, this has not yet been translated to clinical practice and thus women are not receiving RA prior to the age of 50 years when screening is recommended for those at average risk. Women at high risk, in contrast, should start screening as young as age 25 (e.g., for those identified to have a *BRCA1* or *BRCA2* mutation). As most women ages 25-49 years of age do not now receive RA, and breast cancer in these women presents with a more aggressive phenotype at later stage associated with inferior outcomes, implementation strategies for RA in this age group should be developed. If women age 25-49 receive RA and are identified as high-risk, they can be screened earlier than age 50 to diagnose cancer at an earlier stage, when the disease is most successfully treated.

3. Objectives

The central goal of this study is to test strategies to implement evidence-based breast cancer RA in healthcare clinics in Tennessee. The strategies that we will test include engaging a site champion at each clinic, offering tailored provider education, and offering tools to increase patient awareness of breast cancer RA. The BRAVE study aims to assess the feasibility, reach, acceptability, and appropriateness of these select customized strategies to increase uptake of breast cancer RA. We will achieve these aims through a conducting a stepped-wedge trial employing a mixed methods study design. The primary outcome is the proportion of women age 25-49 having RA. Secondary outcomes include the numbers of women: 1) identified as high-risk; 2) pursuing risk-adherent screening; and 3) diagnosed with breast cancer. Implementation outcomes include reach, feasibility, acceptability, and appropriateness. Data collected will inform a future multi-site cluster randomized clinical trial to test the implementation strategies on a larger scale over a longer duration, enriched for underserved populations such as minority and rural dwellers.

4. Personnel

5. Research Design and Methods

5.1 Feasibility

5.1.1 Purpose

Test the feasibility of implementing strategies to increase uptake of breast cancer RA.

5.1.2 Feasibility Assessment

Presentation of Potential Strategies:

The Vanderbilt study team will give a short presentation demonstrating the proposed strategies to increase breast cancer RA. Strategies include engaging a site champion, offering provider education, and offering methods to increase patient awareness of breast cancer RA. The presentation will be either in person or virtual as necessary per COVID restrictions. The presentation is expected to take approximately 15 minutes and will demonstrate strategies such as how a site champion will engage with the research team to share information with clinics, how provider education can be offered to the sites, and how patient awareness materials could be presented.

Following the presentation, the Vanderbilt team will distribute a web-based voluntary, anonymous REDCap survey to clinic providers and staff. This survey is an adapted version of the validated Feasibility of Intervention Measure (FIM), a 4-item scale that measures provider perception that a given practice can be easily or conveniently performed. Questions are asked on a Likert-like scale (1, Completely Disagree – 5, Completely Agree) with both FIM sum and mean scores calculated. Higher scores indicate higher feasibility. **[see REDCap Survey - Feasibility]**

Following completion of the survey, clinic providers and staff will be invited to participate in a brief listening session to share their thoughts on the strategies presented. **[see Listening Session Guide - Feasibility]**

Recruitment and Eligibility: The Vanderbilt study team will perform the Feasibility Assessment in up to 10 clinics in Tennessee. The Vanderbilt team will recruit clinics to participate in the Feasibility Assessment leveraging existing relationships through the TBCSP to identify potential participants **[see Recruitment Email – Feasibility]**. The Vanderbilt team will respond via email or phone to answer additional questions potential clinics may have. The Vanderbilt team will recruit individuals at each participating clinic at the time of the feasibility presentation to participate in the Feasibility Assessment **[see Information Sheet – Feasibility]**. The Vanderbilt team will answer any questions potential participants may have. The survey sample will consist of approximately 60 individuals. Sample size at individual clinics may vary due to differences in the number of providers and staff at each clinic. Eligible individuals will be age 18 and older and will be a provider, staff, or administrator employed in a clinic enrolled in the study.

Data Collection Methods: Data from the anonymous, voluntary survey will be collected and stored via REDCap, a secure online data collection tool. The listening sessions will be digitally recorded via audio recorders with participant permission, transcribed verbatim, and coded by two research team members using a codebook. If participants choose not to be recorded, the interviewer will take notes on their responses. Any identifying information that are part of the participants' responses will be removed from the transcriptions. Original listening session recordings will be destroyed once transcribed. The responses to all the listening sessions will be summarized. When the specific responses from individual organizations are quoted, the organization or person's name will not be identified.

Consent: We will request a Waiver of Consent for the Feasibility Assessment. Consent will be implied by completion of the survey and participation in a listening group.

5.1.3 Data Analysis

Continuous measurements will be summarized using mean + standard deviation or median/interquartile range. tables and graphs will be created to describe and visualize data. Qualitative data will be analyzed using inductive coding to identify emerging themes.

5.2 Reach

5.2.1 Purpose

Conduct a trial to evaluate the impact of breast cancer RA implementation strategies on the proportion of eligible women receiving RA (reach). The intervention in this trial is the use of implementation strategies including identifying a site champion, offering provider education, and providing tools to increase patient awareness of RA. The working hypothesis is that implementing this bundle of selected strategies to increase utilization of breast cancer RA will increase the proportion of eligible women (age 25-49) having RA performed when compared to usual care.

5.2.2 Design

The BRAVE trial is a real-world cross-sectional trial. The trial intervention is the implementation of the bundle of selected strategies to increase uptake of breast cancer RA (Fig. 1). No clinics are exposed to the intervention at the beginning of trial. Subsequently, each clinic will receive the intervention. Data will be collected before and after intervention, so that each clinic contributes observations under both control and intervention conditions. Ultimately, all clinics will receive the same intervention. The primary outcome is the proportion of eligible women (women age 25-49) who receive breast cancer RA.

5.2.3 Implementation Periods (Control, Implementation, Maintenance)

Control: Baseline data on reach will be collected through electronic health record or data collection forms (see section 5.2.6 - Data collection methods).

Implementation: During the implementation period, the research team will identify and engage the site champion and the research team. The research team will deliver tailored in-person provider education and provide clinics with tools to increase patient awareness of breast cancer risk assessment. The research team will also participate in clinic staff meetings to answer questions about breast cancer RA, discuss barriers to performing RA, and provide feedback on the clinic's use of RA. Final versions of education and awareness materials have been submitted and approved by the IRB.

Maintenance: Implementation strategies will no longer be offered. The maintenance period will consist of data collection only.

5.2.4 Recruitment and Eligibility

The Vanderbilt team will recruit 10 individual clinics to participate in the trial. We will apply eligibility criteria to purposively select geographically diverse clinic sites serving racially diverse populations. First, clinics must be located within approximately 2-hour driving distance of Nashville, Tennessee, where the program coordinator is housed to maintain frequent contact with the clinics. Second, clinics must identify a champion to work with the research team and serve as the primary contact. Third, the clinic must serve a racially diverse population of women. Fourth, the clinic must have an electronic health record. We will recruit two back-up clinics meeting these selection criteria in case a site drops out during the early phase of the study. The Vanderbilt team will reach out to potential clinics with the guidance of our established relationship with the TBCSP via email or in person and provide a study information sheet for potential clinics **[see Recruitment Email – Clinic, Information Sheet – Clinic]**. The Vanderbilt team will respond via email or phone to answer additional questions potential clinics may have regarding enrollment.

At the clinics enrolled in the study, we will collect data retrospectively from individual health records on patients who are seen by the clinic. We anticipate that we will collect clinical data on approximately 3,000 women during the time of the stepped-wedge trial. Inclusion criteria for individual records will be women, age 25-49. Exclusion criteria will include personal history of breast cancer.

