5.2.6 Data Collection Methods

Data collection will be performed preferentially through clinic electronic health records. Data will be extracted from the electronic health records through automated reports and through manual chart review. Manual chart review will be performed by individuals affiliated only with the clinic site that the chart is being reviewed for. Individuals will have appropriate data access credentials and IRB approval. VUMC personnel will not directly access any medical records. Data extracted by chart review will be de-identified and entered into the **Clinic Data Collection Form – REDCap**.

If an enrolled clinic does not have a reliable electronic health record, paper data collection forms or via REDCap will be used [**Clinic Data Collection Form – Paper**, **Clinic Data Collection Form - REDCap**]. These clinic data collection forms will be distributed to clinic sites by the research team prior to the initiation of the stepped-wedge trial. Research team personnel will provide instruction to clinic site personnel on how to use the forms. Clinic sites will store the data collection forms in a secure pre-determined location within the clinic. Forms will be electronically scanned and sent to the research team or collected by the research team bi-weekly.

Data collected will include the date of the patient encounter, provider name, demographic information (age, race/ethnicity); was breast cancer RA offered/performed with the Tyrer-Cuzick tool? (yes/no), result of breast cancer RA, was further testing was recommended? (y/n), and what further testing was recommended on the clinical data collection forms. For clinics with reliable electronic health records, this information will be obtained from the electronic health record by participating clinics, deidentified, and provided to the Vanderbilt team. We will obtain data use agreements with the enrolled clinics for the data transfer.

The numerator for the primary outcome (number of women receiving breast cancer RA by Tyrer-Cuzick model) will be extracted by study team members from the electronic health record or data collection form. Study team members will establish the denominator for the primary outcome (number of patients eligible for breast cancer RA) by extracting data on the number of eligible women seen for medical visits at each clinic site from the clinic's electronic medical record or scheduling database.

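### Does naming a site champion at clinic entry expose the control period to part of the intervention?

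*Combined protocol and SAP*

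**What the plan says.** Three sections of the combined protocol and SAP describe how the champion comes into place, and they differ.

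- Section 5.2.4 lists four clinic eligibility criteria. The second is that "clinics must identify a champion to work with the research team and serve as the primary contact". The clinic acts, at entry.
- Section 5.2.3 says: "During the implementation period, the research team will identify and engage the site champion". The research team acts, during implementation.
- Section 5.2.1 defines the treatment under test: "The intervention in this trial is the use of implementation strategies including identifying a site champion". It gives no timing.

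Section 5.2.2 adds that no clinic is exposed when the trial begins and that each clinic contributes data under both conditions. The control paragraph of Section 5.2.3 covers data only: "Baseline data on reach will be collected through electronic health record or data collection forms". It does not mention the champion.

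**The concern.** If identifying a champion is part of the bundle, and every clinic must have done so to be eligible, then no clinic is strictly unexposed during control. That sits badly with Section 5.2.2. No section says what a named champion may do before implementation, and Section 5.1.2 describes the role in general terms as working with the research team to pass information to clinics.

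The primary analysis in Section 5.2.8 compares the proportion of women receiving RA under control and under intervention, and reports an adjusted odds ratio. If a champion began promoting RA on being named, and if that raised use, the control proportion would include part of the effect and the odds ratio would be pulled toward 1. The trial could then understate what the strategies achieve.

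**Working it through.** The documents contain no power calculation and no RA rate, so there is no figure to reproduce. The check is a comparison of passages.

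**1. What is the active component?** Section 3 and Section 5.1.2 both describe the champion strategy as *engaging* a champion. Only Sections 5.2.1 and 5.2.3 use *identify*. The sentence in Section 5.2.3 is also garbled: as printed, the research team is to identify and engage both the champion and itself. It is weak evidence for a separate, second act of identification.

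**2. When does the active component start?** Section 5.2.3 puts engagement of the champion, provider education, patient-awareness tools and attendance at staff meetings in the implementation period. Control contains baseline data collection and nothing else.

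**3. Can the sections be read together?** Yes. The clinic names a contact at entry (5.2.4), and the research team engages that person when implementation begins (5.2.3). On this reading Section 5.2.2 stands as written, and the comparator is usual care, as Section 5.2.1 intends.

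**4. Do control visits follow naming?** Possibly, for some records. Section 5.2.6 says: "If an enrolled clinic does not have a reliable electronic health record, paper data collection forms or via REDCap will be used", and "These clinic data collection forms will be distributed to clinic sites by the research team prior to the initiation of the stepped-wedge trial". An enrolled clinic has already named its champion, so a form completed at a control visit would postdate naming. Two points limit this. Section 5.2.4 requires an electronic health record, so the number of such clinics may be zero. Section 5.2.6 also uses the REDCap form for data from chart review, so the date on which a form was supplied does not fix the date of the visit recorded on it. For data extracted retrospectively from records, the order is not stated.

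**5. Can the effect be sized?** No. Section 5.2.4 states: "We anticipate that we will collect clinical data on approximately 3,000 women during the time of the stepped-wedge trial". An equal split gives 3,000 / 10 = 300 records per clinic. The control share is not given; at an assumed 25%, 50% or 75% it would be 300 × 0.25 = 75, 300 × 0.50 = 150 or 300 × 0.75 = 225 records per form-using clinic, multiplied by a number of such clinics that may be 0. These figures count visits made while a contact had been named. They do not count visits exposed to promotion, and they say nothing about bias.

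**6. Can analysts label encounters without more text?** Yes. Section 5.2.6 provides that "Data collected will include the date of the patient encounter", and each clinic has an implementation period. Encounters before that period starts are control. Labelling them instead by the date on which the champion was activated would gain nothing and could do harm: the champion is one of three components, and if education or tools came first, exposed visits would be labelled control.

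**The case for a change.** The strongest reply is that the two-step reading is an inference: no section states that a named champion stays inactive until implementation. A person chosen for interest in the subject, and told what the study is about, may start talking about RA at once. Retrospective extraction does not rule this out, because control visits may fall after naming, and a sentence forbidding early promotion would cost almost nothing.

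Part of this stands. The verbs are inconsistent, and the control paragraph is silent on the champion. But silence does not license early activity. Section 5.2.1 names usual care as the comparator, Section 5.2.2 denies exposure at the start, and Section 5.2.3 lists the active work under implementation only. A team would have to depart from the plan to produce the contamination described. The argument also assumes that a person who has received no study education or tools would raise RA use, and the documents offer no support for that. Having a known contact at each clinic before data collection begins is an ordinary practical need, particularly where Section 5.2.6 has clinic personnel extract data and complete forms.

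**Conclusion.** This is a clerical inconsistency between *identify* and *engage*, and it leaves the primary comparison intact. Followed as written, the plan keeps the research team's engagement of the champion, the education and the tools out of the control period, and analysts can separate control from implementation encounters by the start of each clinic's implementation period. The size of any bias cannot be determined from the documents; it is zero if named champions act only as contacts until then. Using one verb throughout would be tidier, but no result depends on it.

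The conclusion assumes that the research team follows Section 5.2.3 and that a clinic's implementation start applies to the whole bundle. It covers the supplied text only. Fig. 1, the opening part of the protocol, and the clinic recruitment email and information sheet are not available, and any of them may already state the champion's role or the step dates.

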5.2.5 Remuneration

Clinics will be offered compensation for the administrative time and effort and IT efforts necessary to participate in the study.

5.2.6 Data Collection Methods

Data collection will be performed preferentially through clinic electronic health records. Data will be extracted from the electronic health records through automated reports and through manual chart review. Manual chart review will be performed by individuals affiliated only with the clinic site that the chart is being reviewed for. Individuals will have appropriate data access credentials and IRB approval. VUMC personnel will not directly access any medical records. Data extracted by chart review will be de-identified and entered into the **Clinic Data Collection Form – REDCap**.

If an enrolled clinic does not have a reliable electronic health record, paper data collection forms or via REDCap will be used [**Clinic Data Collection Form – Paper**, **Clinic Data Collection Form - REDCap**]. These clinic data collection forms will be distributed to clinic sites by the research team prior to the initiation of the stepped-wedge trial. Research team personnel will provide instruction to clinic site personnel on how to use the forms. Clinic sites will store the data collection forms in a secure pre-determined location within the clinic. Forms will be electronically scanned and sent to the research team or collected by the research team bi-weekly.

Data collected will include the date of the patient encounter, provider name, demographic information (age, race/ethnicity); was breast cancer RA offered/performed with the Tyrer-Cuzick tool? (yes/no), result of breast cancer RA, was further testing was recommended? (y/n), and what further testing was recommended on the clinical data collection forms. For clinics with reliable electronic health records, this information will be obtained from the electronic health record by participating clinics, deidentified, and provided to the Vanderbilt team. We will obtain data use agreements with the enrolled clinics for the data transfer.

The numerator for the primary outcome (number of women receiving breast cancer RA by Tyrer-Cuzick model) will be extracted by study team members from the electronic health record or data collection form. Study team members will establish the denominator for the primary outcome (number of patients eligible for breast cancer RA) by extracting data on the number of eligible women seen for medical visits at each clinic site from the clinic's electronic medical record or scheduling database.

Data collection for secondary outcomes will include the number of women offered RA, but declining; number of high-risk women identified; number of high-risk women pursuing risk-stratified screening; number of abnormal screening studies; number of cancers identified; and types of cancers identified. Data on these secondary outcomes will be obtained from the electronic health record. This data will be collected for 6 months following the completion of the stepped wedge trial.

Additional secondary outcomes of adoption and maintenance will be extracted from the electronic health record or data collection forms (described in section 5.2.6) by Vanderbilt research team members. Adoption outcomes will include the total number of clinics offering RA and the total number of providers offering RA during the implementation phase. Maintenance outcomes will include the total number of clinics offering RA and the total number of providers offering RA six months after the completion of the implementation period.

Data will be collected during the control, implementation, and maintenance time periods of the stepped-wedge trial.

5.2.7 Consent

As enrollment will occur at the clinic level, rather than the individual level, and the study intervention is considered usual care, consent from individual participants will not be obtained. We will use a data use agreement to obtain data from the electronic health record and the clinic data collection forms from the enrolled clinics.

5.2.8 Data Analysis

Data will be summarized using mean +/- standard deviation. Generalized linear mixed models for binary outcome will be used to assess difference in the proportion of participants receiving breast cancer RA between control and intervention groups, stratifying by clinic size, rural vs. urban location, race/ethnicity, socioeconomic status, and time, with a nested random-effect for subjects within clinic clusters. Adjusted odds ratio (OR) with 95%

confidence interval (CI) will be reported. Interaction between intervention and time will be assessed. All tests of statistical significance will be two-sided. Findings will be considered significant if $p < 0.05$.

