6.2 Reach

The Vanderbilt team will recruit and enroll a total of 10 healthcare clinics across the state of Tennessee to participate and will collect data on reach and clinical outcomes. Recruitment will occur via email and via personal contact using established local connections. Individual women will NOT be enrolled in the study or consented as the study intervention is considered usual care. At the clinics enrolled in the study, we will collect data from individual health records on women patients who are seen by the clinic. We anticipate that we will collect clinical data on approximately 3,000 individual women ages 18-49 during the time of the stepped-wedge trial. We will obtain a HIPAA waiver to collect data from the electronic medical record.

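### Age is collected but is not in the primary model, so a change in a clinic's age mix that coincides with crossover could bias the intervention odds ratio

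*Combined protocol and SAP*

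**What the plan says.** **Model.** Section 5.2.8 specifies a generalized linear mixed model for the binary outcome, "stratifying by clinic size, rural vs. urban location, race/ethnicity, socioeconomic status, and time", and "with a nested random-effect for subjects within clinic clusters". An adjusted OR with a 95% confidence interval is reported, and the intervention-by-time interaction is examined. I read the stratifying terms as adjustment covariates, because the reported OR is an adjusted one. Age is not among them.

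**Data.** Section 5.2.6 includes "demographic information (age, race/ethnicity" among the items to be collected, so one of these two items enters the model and the other does not. No reason is given. The same section builds the denominator by "extracting data on the number of eligible women seen for medical visits at each clinic site", from the electronic record or the scheduling database.

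**Design.** Section 5.2.2 states: "The BRAVE trial is a real-world cross-sectional trial". It adds: "Data will be collected before and after intervention, so that each clinic contributes observations under both control and intervention conditions".

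**Age range.** Section 5.2.4 says: "Inclusion criteria for individual records will be women, age 25-49". Section 6.2 instead refers to "approximately 3,000 individual women ages 18-49 during the time of the stepped-wedge trial".

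**The concern.** The intervention effect is estimated mainly from before-and-after contrasts within clinics. The records on either side of a clinic's crossover come from whichever women attended at the time, so nothing in the design holds their age distribution constant across a band of 25 single-year ages.

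Two of the remaining terms help only in part. The clinic effect absorbs stable differences in age between clinics. The time terms absorb calendar changes common to all clinics, provided that clinics cross over at different times. Neither removes an age shift inside a clinic that arrives together with the strategies. If all clinics start at once, time cannot separate a general drift in age from the intervention. The name stepped-wedge, used in several sections, implies staggered starts, but the text of Sections 5.2.2 and 5.2.3 gives no step times and no random order.

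At stake is whether the primary OR reflects a change in practice or partly a change in who was seen. Adjusting for age after the data are in would look post hoc.

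**Working it through.** The protocol gives no RA rate by age, baseline RA rate, expected effect or intraclass correlation, so there is no figure of its own to reproduce. This is an illustration of bias under a true OR of 1.00.

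**Inputs from the protocol:** 10 clinics (Sections 5.2.4 and 6.2); about 3,000 women (same sections); ages 25-49 (Section 5.2.4).

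**Assumed inputs:** 40% of women aged 40-49 before crossover; RA rates below 40 and at 40-49 of 5% and 8% (weak gradient), 10% and 20% (middle), or 10% and 30% (strong); a rise of 5, 10 or 20 points in the share aged 40-49.

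**Step 1: crude before/after contrast.** With share s aged 40-49,

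P(s) = p_young × (1 − s) + p_old × s, and OR = odds of P(s_after) ÷ odds of P(s_before).

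- Weak gradient, before: 0.05 × 0.60 + 0.08 × 0.40 = 6.20%. After a 20-point rise: 0.05 × 0.40 + 0.08 × 0.60 = 6.80%. OR = (0.068/0.932) ÷ (0.062/0.938) = 1.10.
- Strong gradient, before: 0.10 × 0.60 + 0.30 × 0.40 = 18.0%. After a 10-point rise: 0.10 × 0.50 + 0.30 × 0.50 = 20.0%. OR = (0.20/0.80) ÷ (0.18/0.82) = 1.14.

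| RA rate <40 / 40-49 | +5 points | +10 points | +20 points |
|---|---|---|---|
| 5% / 8% | 1.03 | 1.05 | 1.10 |
| 10% / 20% | 1.04 | 1.08 | 1.17 |
| 10% / 30% | 1.07 | 1.14 | 1.29 |

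The spurious difference is the shift times the rate gap: 0.15 to 0.6 points, 0.5 to 2 points and 1 to 4 points for the three rows. If either factor is zero, so is the bias.

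**Step 2: do clinic and time terms remove it?** Logistic regression was fitted to expected counts, without noise, for 10 clinics × 6 periods × 50 women = 3,000. The number of periods is assumed, the clinics are otherwise identical, and fixed clinic terms stand in for the random effect. RA rates are 10% and 30%, and the shift is 10 points.

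| Shift in age mix | Crossover | OR without age | OR with age |
|---|---|---|---|
| At each clinic's own crossover | Staggered, period terms | 1.14 | 1.00 |
| At crossover | All together, no separable period terms | 1.14 | 1.00 |
| Gradual, common to all clinics | Staggered, period terms | 1.00 | 1.00 |
| Gradual, common to all clinics | All together, no separable period terms | 1.08 | 1.00 |

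For shifts of 5 and 20 points, the staggered model without age gives 1.07 and 1.29 when the shift is at crossover. The last row without age becomes 1.04 and 1.16.

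The last row can be checked by hand. A linear rise of 10 points over six periods, with crossover after the third, gives mean shares of 42% before and 48% after. The rates are then 18.4% and 19.6%, and the OR is (0.196/0.804) ÷ (0.184/0.816) = 1.08.

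**Step 3: chance alone.** For 1,500 versus 1,500 women at a 40% share, ignoring clustering, the standard error of the difference in share is √(2 × 0.4 × 0.6 / 1,500) = 1.8 points. With the strong gradient, one such standard error moves the rate by 0.018 × 0.20 = 0.36 points, from 18.0% to 18.36%, an OR of about 1.02.

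**The case against.** The strongest reply is that nothing in the protocol shows that the bias will occur. It needs RA rates that differ by age within 25-49 and an age shift tied to crossover; the documents show neither. The background text before Section 3 describes under-use across the whole band, and its screening threshold of 50 lies outside the band. Chance is an unlikely source of the larger shifts, since 10 points is over five of the standard errors above. Patient-awareness tools (Section 5.2.3) might change who attends, but the protocol does not describe outreach to women who would otherwise not come. Clinic and time terms already deal with stable clinic differences and, under staggered crossover, with drift common to all clinics. All of this stands, and it limits the size and the certainty of the point.

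Three stronger readings are tempting, and the documents do not support them. A reader might infer that an age shift will be counted as an intervention effect; the documents support only that it could be. A reader might take wholly different women to be sampled in each period; the subject-level random effect in Section 5.2.8 suggests that a woman may contribute more than once. A reader might assume that age is held for every record; Section 5.2.6 describes the denominator as a number of women and does not say that each woman's age is transferred.

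The reply does not defeat the recommendation. Age must be known at the clinic to decide eligibility, and a model with race/ethnicity already needs individual data on women without RA. Age adds little to that burden and removes the bias in every scenario tabulated in Step 2.

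**Conclusion.** The omission is certain: age is collected, is not in the stated model, and is not added elsewhere. The bias is conditional and its size is unknown. It requires an RA rate that varies with age, together with either a change in age mix that coincides with crossover or a calendar shift when clinics do not cross over at staggered times.

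The OR ranges of 1.03-1.10 (weak gradient) and 1.07-1.29 (strong gradient) are unadjusted illustrations on assumed rates and shifts, not predictions for this trial. They also describe a rise in the share of older women; a fall would push the OR the other way. Prespecifying age is a worthwhile, low-cost improvement to the primary analysis. The point does not show that the planned analysis is invalid.

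**What to change.** 1. In Section 5.2.8, add age at the visit as a prespecified fixed effect in the primary model. A spline in years or a few bands would do; the form is a matter of choice, but should be fixed before data are examined.
2. Tabulate age by clinic and period, so that a shift at crossover can be seen.
3. In Section 5.2.6, state that individual age is extracted and transferred for all women in the denominator, including those without RA. Age in years is enough.
4. Reconcile the age ranges in Sections 5.2.4 and 6.2, so that the age term is defined over the population actually analysed.
5. In the same check of the extract, confirm the source of socioeconomic status, which is in the model but not among the data items listed in Section 5.2.6.

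The cost is a line in the analysis section, 1-3 degrees of freedom against about 3,000 records, and a check of the data extract. If age turns out not to be transferred for women without RA, the extract specification must be extended, which is easier to do before collection is complete.
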